7.3.3 Overall Survival

Analysis methods are the same as those described for PFS in Section 7.2.1.

8 Safety Analysis

Safety data will be summarised using appropriate summary statistics (i.e. mean, standard deviation, median, and range for continuous variables, and number and proportion of patients for categorical variables). Summaries will be presented for the SS population. The baseline value of any variable will be defined as the last available value prior to the first administration of study treatment.

8.1 Extent of Exposure

Sometimes the doses are recalculated on Aria - prescribing system if there has been a change in creatinine- these lead to minor changes and hence they are not counted as dose-reduction as they are all less than 10%. Exposure data will be summarised, indicating total exposure to study drug, as well as the number of any dose reductions.

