**All PET CT scans will be performed at (or sent to) University College Hospital to be centrally reviewed.**

### **3.2 Treatment plan**

Carboplatin will be administered as a day case and doses will be calculated using the Calvert formula as below:

$$\text{Dose (mg)} = (\text{GFR} + 25) \times 10$$

Unless dictated by haematological toxicity, the Carboplatin dose should not be recalculated for each cycle. However, if the serum Creatinine has risen by > 20% above baseline, the Carboplatin dose must be recalculated using the Calvert formula with GFR determined by EDTA clearance. At the discretion of the PI an estimated creatinine clearance can be calculated using e.g. Cockcroft and Gault (or as per local policy) if the site is unable to obtain EDTA clearance.

Treatment will be repeated every 3 weeks (when platelets over  $100 \times 10^9/L$ , white blood count greater than  $3 \times 10^9/L$  or neutrophils greater than  $1 \times 10^9/L$ ).

If the blood count is below the level required to commence the next cycle of treatment (i.e. platelets less than  $100 \times 10^9/L$ , white blood count less than  $3 \times 10^9/L$  or neutrophils less than  $1 \times 10^9/L$ ) then a further blood count must be repeated 48 hours after the target treatment day. If the results of this repeat count show platelets greater than  $75 \times 10^9/L$  and rising, white blood count greater than  $3 \times 10^9/L$  or the neutrophils greater than  $1 \times 10^9/L$  the patient may commence to the next cycle [See Figure 1].

If neutrophils are less than  $1 \times 10^9/L$  and white blood count less than  $3 \times 10^9/L$ , filgrastim or lenograstim (GCSF) should be given for 2 days.

However, if the blood count remains below the level required it should continue to be monitored at 48 hour intervals until it has reached the required level for proceeding with further treatment (platelets are greater than  $75 \times 10^9/L$  and rising, white count greater than  $3 \times 10^9/L$  or the neutrophils are greater than  $1 \times 10^9/L$ ).

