## **4.0 *Eligibility, subject selection and withdrawal***

### **4.1 *Inclusion Criteria***

1. Metastatic seminoma-IGCCCG good prognosis.
2. Glomerular filtration rate by EDTA clearance over 25 ml/min (a measured creatinine clearance using Cockcroft and Gault would be allowed if unable to perform EDTA clearance).
3. ECOG Performance status 0-3.
4. Normal Alpha-fetoprotein (All levels of Human chorionic gonadotropin and Lactate dehydrogenase are acceptable).
5. Males aged  $\geq 18$  and  $\leq 75$  years.
6. Able to give written informed consent prior to study entry.
7. Patients must be sterile or agree to use adequate contraception during the period of therapy.

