6.5 Treatment Compliance

Treatment compliance will be presented for all patients in the SS in terms of:

- Median and range for each cycle length.
- Frequency and percentage of patients having a dose reduction.

- Frequency and percentage of patients having a dose reduction due to low platelet count (<20).
- Frequency and percentage of patients discontinuing investigational medicinal product (IMP).
- Frequency and percentage of patients leaving the study due to disease progression or death.

7 Efficacy Analysis

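### SAP 8.1 leaves every creatinine-driven dose recalculation out of the dose-reduction count as under 10%, a premise that the protocol's dose formula and >20% creatinine trigger do not support

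*SAP*

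**What the plan says.** SAP 8.1 introduces the recalculations this way: "Sometimes the doses are recalculated on Aria - prescribing system if there has been a change in creatinine". It calls the resulting changes minor and states that "they are not counted as dose-reduction as they are all less than 10" per cent. It sets no limit on the size of the creatinine change, makes no exception for a larger dose change, and does not name the reference dose for the percentage. It then plans summaries of total exposure and of the number of dose reductions. SAP 6.5 reports "Frequency and percentage of patients having a dose reduction", with a separate line for reductions due to low platelets.

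Protocol 3.2, repeated in 6.5, sets the default: "Unless dictated by haematological toxicity, the Carboplatin dose should not be recalculated for each cycle". The exception is that "if the serum Creatinine has risen by > 20% above baseline, the Carboplatin dose must be recalculated using the Calvert formula", with GFR measured by EDTA clearance. Where a site cannot obtain that, "At the discretion of the PI an estimated creatinine clearance can be calculated using e.g. Cockcroft and Gault".

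**The concern.** The SAP excludes by cause and justifies the exclusion by size. That works only if the cause guarantees the size. The protocol's own rule makes recalculation mandatory after a creatinine rise above 20%, and for most plausible GFR values a creatinine-based estimate then gives a cut of 10% or more. Read literally, the SAP would leave such a cut out of the reduction count.

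The count matters because tolerability of AUC-10 is part of the stated objective and the reduction tables are a main readout of delivered dose. Total exposure does not replace them: patients receive 3 or 4 cycles at individually calculated doses, and SAP 8.1 does not relate the total to the planned dose. The SAP's abbreviation list includes percentage intended dose and relative dose intensity, but the text available for review specifies no analysis of either.

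**Working it through.** **Inputs**

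- Dose (mg) = (GFR + 25) x 10: Protocol 3.2 and 6.5.
- Mandatory recalculation when creatinine has risen by more than 20%: same sections.
- Eligible GFR: "Glomerular filtration rate by EDTA clearance over 25 ml/min", with no upper limit (Protocol 4.1).
- Rounding to the nearest 10 mg (Protocol 6.5). This moves a dose by at most 5 mg, or 0.4% of 1250 mg.
- The SAP's figure: every change under 10% (SAP 8.1). No derivation is given, so the check asks when the formula and trigger produce it.
- Assumption, not in the documents: GFR is proportional to 1/creatinine, with age and weight constant, as in a creatinine-based estimate.

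**Step 1. Cut for a fractional creatinine rise r.** New GFR = GFR/(1 + r), so

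cut = 1 - [GFR/(1 + r) + 25]/(GFR + 25) = [r/(1 + r)] x GFR/(GFR + 25).

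At r = 0.20 this is (1/6) x GFR/(GFR + 25). At GFR 100, for example, it is (1/6) x 100/125 = 13.3%.

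| Baseline GFR (ml/min) | Starting dose (mg) | Dose after 20% rise (mg) | Cut at 20% rise | Cut at 30% rise |
|---|---|---|---|---|
| 25 | 500 | 458 | 8.3% | 11.5% |
| 37.5 | 625 | 562.5 | 10.0% | 13.8% |
| 60 | 850 | 750 | 11.8% | 16.3% |
| 100 | 1250 | 1083 | 13.3% | 18.5% |
| 120 | 1450 | 1250 | 13.8% | 19.1% |

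The trigger is a rise of more than 20%, so the fourth column is a lower bound for trigger-driven cuts under this assumption.

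**Step 2. Where the SAP's figure holds at the trigger.** Setting (1/6) x GFR/(GFR + 25) = 0.10 gives GFR/(GFR + 25) = 0.6, so GFR = 37.5. At exactly a 20% rise, the cut is under 10% only for baseline GFR below 37.5.

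**Step 3. The rise that gives a 10% cut.** The GFR fall needed is 0.10 x (GFR + 25)/GFR, and the matching creatinine rise is 1/(1 - fall) - 1.

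- GFR 60: fall 14.2%, rise 16.5%
- GFR 100: fall 12.5%, rise 14.3%
- GFR 120: fall 12.1%, rise 13.7%

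Under the same assumption, then, a cut below 10% at these GFR values comes from a creatinine rise below the protocol's trigger.

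**Step 4. Weaker GFR response.** A measured GFR need not fall in proportion. Taking new GFR = GFR/(1 + r)^e at r = 0.20:

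| Baseline GFR | e = 1 | e = 0.75 | e = 0.5 |
|---|---|---|---|
| 60 | 11.8% | 9.0% | 6.2% |
| 100 | 13.3% | 10.2% | 7.0% |
| 120 | 13.8% | 10.6% | 7.2% |

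Over GFR 25 to 150, the cut at a 20% rise is 6.4% to 11.0% for e = 0.75 and 4.4% to 7.5% for e = 0.5. A cut under 10% at the trigger is therefore possible with EDTA, but not assured.

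**The case against.** The strongest reply is that SAP 8.1 reports what was seen on the prescribing system: the changes were minor and all below 10%. If that is true of every recalculation, no cut of 10% or more is lost. A reader might infer from the arithmetic that reductions have in fact been undercounted. The documents do not support that, because nothing in them shows a patient passing the >20% trigger. The protocol's first-choice GFR on recalculation is also EDTA clearance, for which the proportional assumption may overstate the fall. Both points stand, and they make the omission conditional.

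A reader might also infer that recalculations under 10% were protocol deviations that the SAP conceals. That goes too far. The protocol says the dose should not be recalculated for each cycle, which does not plainly bar a single response to a smaller creatinine change. SAP 5.2.2 already tabulates and lists important deviations, and SAP 8.1 exempts nothing from it. What remains is that the SAP does not say how these recalculations are classified.

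Finally, the effect is confined to descriptive tables. Total exposure, platelet-driven reductions and drug discontinuations are still reported. This limits the point's weight but does not make the premise sound.

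**Conclusion.** The point holds in conditional form. SAP 8.1 writes an unlimited exclusion into the plan on a premise that Protocol 3.2 and 6.5 do not guarantee. With creatinine-based GFR, a recalculation at the mandatory trigger cuts the dose by 10% or more from baseline GFR 37.5 upwards, reaching 13.8% at 120 and more for larger rises. At exactly a 20% rise it is below 10% for GFR 25 to 37.5, and it could be below 10% at higher GFR if the measured value falls less than proportionally. Any cut of 10% or more would be missing from the counts in SAP 6.5 and 8.1; whether any occurred cannot be told from the documents. The PFS analysis and its decision rule are not touched.

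**What to change.** Replace the cause-based exclusion in SAP 8.1 with a size-based counting rule. Count as a dose reduction any administered dose 10% or more below the cycle 1 dose, whatever the cause, and tabulate by reason: platelet nadir, creatinine recalculation, other. Show smaller creatinine-driven changes in a separate line. Use the same definition in SAP 6.5.

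Reconcile SAP 8.1 with Protocol 3.2 and 6.5 on recalculations made below the >20% trigger, and state whether they count as deviations under SAP 5.2.2. This review takes no view on which dosing rule is right.

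The cost is SAP wording. The rule needs the administered dose and the reason for change at each cycle. The case report form is not among the documents, so check that both are captured. The reported reduction rate may come out slightly higher. If every creatinine-driven change was under 10%, that part of the count stays at zero and can be verified.

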8.2 Adverse Events (AEs)

AEs, irrespective of relatedness, will be summarised. Verbatim descriptions of treatment-emergent AEs will be mapped to the appropriate thesaurus terms and summarised by mapped MedDRA term, and national cancer institute (NCI) CTCAE grade. For each patient's AE, the maximum severity reported will be used in the summaries. SAEs, including deaths, will be summarised separately. Specifically, the following descriptive statistics will be generated.

1. Incidence of SAEs.
2. Incidence of grade 3 and 4 AEs (CTCAE, version 4.03).
3. Incidence of all AEs of all grades.

8.3 Deaths, Serious Adverse Events (SAEs) and other Significant Events

All deaths, SAEs and other significant events will be summarised in line listings. SAEs will be reconciled with the AEs.

8.4 Clinical Laboratory Evaluations

Laboratory data will be tabulated, with values outside normal ranges identified and summarised by NCI CTCAE (Version 4.03) grade. Barts Normal ranges will be used as reference. The worst condition for each patient during the entire treatment will be reported.

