- 11. *The hormone tests should be performed at baseline, end of treatment and annually at follow ups.*

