### **11.6 Secondary endpoint analysis**

Subgroup analyses of the PFS rate will be performed in terms of patients with complete or partial response at 2 years.

The analysis of safety will include all patients who received at least one cycle of treatment. Safety and tolerability of Carboplatin AUC-10 will be assessed in terms of changes in laboratory parameters, vital signs, the incidence and severity of Adverse Events, and of toxicities according to the CTCAE classification (version 4.03).

The proportion of patients at each toxicity grade (0 to 4) of any type (including vomiting, nausea and diarrhoea) will be summarised. Safety analysis will be performed based on safety data set.

Metabolic response rate will be assessed as described in section 5.3.3.

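### SAP 8.4 summarises each patient's worst on-treatment laboratory result without comparison to baseline, and the SAP specifies no analysis of follow-up laboratory or hormone results

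*SAP*

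**What the plan says.** **The commitment.** Protocol 11.6 states: "Safety and tolerability of Carboplatin AUC-10 will be assessed in terms of changes in laboratory parameters". The synopsis commits to the same thing.

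**The specified analysis.** SAP 8.4 has two outputs. The first is a general one: "Laboratory data will be tabulated, with values outside normal ranges identified and summarised by NCI CTCAE (Version 4.03) grade". The second is the patient-level summary: "The worst condition for each patient during the entire treatment will be reported". Neither mentions baseline, change, visit or follow-up.

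**The baseline.** SAP section 8 covers all safety data in general terms ("Safety data will be summarised using appropriate summary statistics") and defines a reference value: "The baseline value of any variable will be defined as the last available value prior to the first administration of study treatment". Section 8.4 does not use it. SAP 8.5.1, by contrast, summarises changes in vital signs by scheduled time.

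**Who can enter, and what is collected.** Protocol 4.1 admits men with a GFR just over 25 ml/min, and on markers says "All levels of Human chorionic gonadotropin and Lactate dehydrogenase are acceptable". The flowchart in protocol 5.4 schedules blood counts, U&E and LFTs at end of treatment and at follow-up visits (2-monthly in year 1, 4-monthly in year 2). Its footnote on hormones reads: "The hormone tests should be performed at baseline, end of treatment and annually at follow ups".

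**The concern.** A worst grade and a change from baseline answer different questions. The first asks how abnormal a man's result was at its worst while on treatment. The second asks how far it moved after he started carboplatin. The protocol promises the second; the SAP specifies the first.

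The difference matters here for two reasons. There is no control arm to show the background rate of abnormal results. The entry criteria also allow tests to be abnormal at the start, through disease (LDH, hCG) or limited renal function.

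The second gap concerns time. Protocol 1.1 offers the apparent absence of long-term renal problems with single-agent carboplatin as part of the case for it. The trial collects U&E for two years after treatment, yet no section of the SAP says how those results will be summarised. The same applies to the hormone tests. Routine adverse event recording under protocol 7.3 stops 30 days after the last dose, so scheduled follow-up bloods are the main systematic source on late change.

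**Working it through.** The documents give no figure for this analysis, so there is none to reproduce. The check has three parts.

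**1. Commitment against specification**

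| Item | Adverse events (SAP 8.2) | Vital signs (SAP 8.5.1) | Laboratory (SAP 8.4) |
|---|---|---|---|
| Baseline or emergence rule | treatment-emergent | changes | none |
| Time points | none named | scheduled times | whole treatment period, worst value |
| Follow-up after treatment | not named | not named | not named |

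The SAP applies a reference to the pre-treatment state in the sections on either side of 8.4, but not in 8.4 itself.

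**2. What a worst-grade table can hide**

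Let b be the proportion abnormal at entry, with all such abnormalities persisting, and q the proportion of the remainder who become abnormal on treatment. Then:

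- proportion abnormal in the worst-grade table = b + (1 − b)q
- proportion newly abnormal = (1 − b)q
- men carried in from baseline = b × 50, taking the safety set at its maximum of 50

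Neither b nor q is in the documents. With q assumed at 10%:

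| b | Worst-grade table | Newly abnormal | Carried in, of 50 |
|---|---|---|---|
| 5% | 0.05 + 0.95 × 0.10 = 14.5% | 9.5% | 2.5 |
| 20% | 0.20 + 0.80 × 0.10 = 28% | 8% | 10 |
| 40% | 0.40 + 0.60 × 0.10 = 46% | 6% | 20 |

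Across these rows the table's percentage more than triples while the newly abnormal percentage falls.

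A separate baseline table does not resolve this. Take the middle row: 10 of 50 abnormal at entry and 0.28 × 50 = 14 abnormal at worst. If all 10 persisted, 14 − 10 = 4 men are new. If none persisted, all 14 are new. The two margins allow anything from 4 to 14; only the cross-tabulation settles it.

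**3. How much scheduled data has no named analysis**

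Follow-up visits: 12/2 + 12/4 = 6 + 3 = 9 per man. Post-baseline draws per man, counted from the flowchart:

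| Test | During cycles (3 or 4 cycles) | End of treatment | Follow-up | Follow-up share |
|---|---|---|---|---|
| Full blood count | 6 or 8 | 1 | 9 | 9/16 = 56% or 9/18 = 50% |
| U&E and LFT | 5 or 7 | 1 | 9 | 9/15 = 60% or 9/17 = 53% |
| Testosterone, FSH, LH | 0 | 1 | 2 | 2/3 = 67% |

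Protocol 5.3.2 lists in-cycle U&E and LFT on Day 1 of cycles 2–4 only (2 or 3 draws). On that schedule the follow-up share is 9/12 = 75% or 9/13 = 69%.

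Follow-up therefore holds half or more of the scheduled post-baseline results. A during-treatment summary contains no scheduled in-cycle hormone value; at most it takes in the end-of-treatment sample, if the treatment period is read to include that visit. With 50 men and complete follow-up, the maximum is 9 × 50 = 450 scheduled visits with bloods.

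**The case against.** The strongest reply is that the worst-condition sentence is one output among several. SAP 8.4 also tabulates laboratory data with no time limit, SAP section 8 offers means, medians and ranges for safety variables, and protocol 11.3 says laboratory data will be analysed and summarised. This stands, and it rules out three stronger readings.

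- **That the SAP reports nothing but worst values.** It does not say so; the general tabulation is there.
- **That entry abnormalities will be counted as AUC-10 toxicity.** A reader might infer this, but 8.4 does not attribute laboratory grades to the drug. The toxicity endpoint in SAP section 2 is built on grade 3 or 4 adverse events, and SAP 8.2 refers to treatment-emergent events. The supportable statement is that the two kinds of abnormality cannot be told apart in the table.
- **That follow-up and hormone results are dropped.** The SAP is silent on them; it does not exclude them, and the tabulation could cover them.

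Two further points also stand. GFR is scheduled only before treatment, so a low entry GFR cannot itself be a worst on-treatment value; only creatinine could carry the problem over. And SAP 6.2 summarises baseline LDH, tumour markers and clearance, so readers will see how many men entered with those abnormal. As shown above, that margin does not reveal who worsened, and SAP 6.2 does not list blood counts, LFTs or serum creatinine.

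Finally, the analyses are described as exploratory, and toxicity is a secondary endpoint. That limits the importance of the point. It does not supply the missing analysis: a general promise of suitable statistics names no change, visit or window, and so does not meet the commitment in protocol 11.6.

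**Conclusion.** The point holds as a mismatch between protocol and SAP, together with a gap in the SAP. The protocol promises changes in laboratory parameters. The only patient-level summary specified is a worst on-treatment condition without reference to baseline, and in a single-arm trial that cannot separate a persisting entry abnormality from a new one. No analysis is specified for blood counts, U&E and LFTs from nine follow-up visits, or for testosterone, FSH and LH.

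The number of men affected cannot be fixed from the documents. If 5% to 40% of up to 50 men have a given test abnormal at entry and all persist, about 2 to 20 are carried into the table; with less persistence there are fewer. The follow-up shares (50% or more) are firmer, because they come from the flowchart, but they assume that every scheduled draw is taken.

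This weakens the reporting of a stated safety objective. It has no bearing on the rule of at least 39 progression-free men out of 45. It is worth correcting before database lock, so that laboratory summaries are not chosen after the data are seen.

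**What to change.** In SAP 8.4, for the safety set:

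1. Replace the worst-condition sentence with a shift table, for each test, of baseline CTCAE grade against worst post-baseline on-treatment grade, using the baseline already defined in SAP section 8. State where the on-treatment window ends, including whether the end-of-treatment sample belongs to it.
2. Add summaries of change from baseline at end of treatment, 1 year and 2 years for creatinine, blood counts, LFTs, testosterone, FSH and LH, with the number of men contributing at each time point.

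Change by visit alone would satisfy the wording of protocol 11.6. The shift table is preferable for the graded data because it shows directly who worsened.

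The cost is a few extra descriptive tables and their programming. No visit, sample or treatment changes, and all the data are already scheduled. Follow-up summaries will rest on fewer men where visits are missed, which is why the denominators should be shown.

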8.5 Other Safety Measures

8.5.1 Vital Signs

Changes in vital signs data (if applicable) will be summarised by scheduled measurement time. Vital signs will include height (cm), weight (kg), temperature (degrees Celsius), blood pressure, respiratory rate, and heart rate.

ECOG performance score will also be summarised by scheduled time point.

9 Reporting Conventions

The mean, standard deviation, and any other statistics other than quantiles, will be reported to one decimal place greater than the original data. Quantiles, such as median, or minimum and maximum will use the same number of decimal places as the original data.

10 Technical Details

Analysis will be conducted using Stata v 13 (or subsequent versions). A second statistician will independently double check the statistical codes for the main endpoints of analysis following our Statistical standard operation procedure (SOP).

This SAP is based on Car-PET Protocol: Master Version 8.0 dated 31st August 2017. All programs will be stored in the *G:\Experimental Cancer Medicine\Statistics\Inhouse Unblinded\Car-PET* folder until the end of the study at which point they will be merged with the trial master file (TMF) for archiving.

11 Summary of Changes to the Protocol

12 References

3. A'Hern RP: Sample size tables for exact single-stage phase II designs. Stat Med 2001; 20(6): 859-66.
